
DLT PERIOD AND DEFINITION OF DLTS
	
The DLT period is defined as Cycle 1*.
 
DLT is defined as any of the following treatment-emergent adverse events (TEAEs) which are possibly, probably or definitely related to the combination treatment and occurring in Cycle 1 (1 cycle=4 weeks):
 
 
• Any Grade 4 or 5 hematologic toxicity, clinical or laboratory non-hematologic toxicity
 
• Febrile neutropenia any grade, Grade 3 thrombocytopenia if associated with bleeding or requiring platelet transfusion
 
• Grade 2 or higher cardiac or neurologic toxicities, pneumonitis that does not resolve within 3 days after starting steroids at adequate doses or that was recurrent upon steroid tapering or withdrawal, myasthenia gravis, myositis, polymyositis, Guillain-Barre syndrome (excluding peripheral purely-sensory neuropathies)
 
• Grade 2 or higher alanine transaminase (ALT)/ aspartate transaminase (AST) increase with a concurrent increase of total bilirubin <math>\geq 2</math> x upper limit of normal (ULN) and concurrent with alkaline phosphatase (ALP) <math>\leq 2</math> x ULN (Hy's law), in the absence of objective causes of biliary obstruction due to obvious disease-related causes
 
• Any other Grade 3 non-hematologic, treatment-related clinical toxicity lasting 3 or more days despite optimal supportive care, or requiring admission for appropriate medical management; hypersensitivity and/or infusion-related reactions are excluded if not reoccurring after appropriate pre-medication and/or prolonging infusion time
 
• Grade 3 non-hematologic laboratory value (excluding lipase, amylase and/or autoimmune endocrinopathies manageable by replacement therapies) if:             
 
a. Symptomatic and
 
b. Medical intervention was promptly required to treat the patient, or
 
c. The abnormality led to hospitalization or
 
d. The abnormality did not resolve to at least Grade 1 within 2 weeks (including the steroid tapering period) despite adequate medical intervention/treatment
 
 
 
• A delay of >2 weeks due to drug-related toxicity in initiating Cycle 2
 
• Unable to complete at least 70% of the scheduled treatment, i.e., more than six Debio 1143 skipped doses in Cycle 1 due to treatment-related toxicity
 
• Required dose reduction in Cycle 1 or on Cycle 2 Day 1 or requirement for treatment withdrawal due to treatment-related toxicity (even if not meeting other DLT criteria)
 
 
* Any toxicity fulfilling one or more of these criteria but occurring from C2D1, may be defined as delayed DLTs after discussion and agreement between Principal Investigators (PIs), DSMC and the Sponsor, and may be considered for RP2D definition, if appropriate.

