
TREATMENT DURATION
	
Participants are planned to be treated with Debio 1143 and nivolumab for up to 52 weeks (13 cycles), until any of the following events occurs: symptomatic PD, asymptomatic but confirmed PD (as per iRECIST), unacceptable toxicity per Investigator judgment and despite up to two dose adjustments, patient withdrawal, or treatment delay greater than 4 and 8 weeks (+1 week tolerance) for Debio 1143 and nivolumab, respectively.
 
Permission to prolong the study treatment for one additional year can be exceptionally granted by the Sponsor, if patients are deriving continuous clinical benefit from the study treatment. Medical justification for extending the treatment and the assessment of the risk/benefit balance must be provided by the Study Investigator and will be discussed with the Sponsor. The decision to further extend study treatment will be re-evaluated on a yearly basis for each patient.
 
Re-treatment criteria are listed in Table 2.
 
From Cycle 2, if a patient does not meet the requirements for treatment continuation on Day 1 of any cycle, both study drugs will be withheld until recovery or for a maximum of 4 and 8 weeks (+1 week tolerance window) for Debio 1143 and nivolumab, respectively. After this delay-period, the patient should withdraw from treatment.
 
If a patient does not meet the requirements for treatment continuation on any days other than D1 (D2-10 or D15-24), treatment will be immediately interrupted and the corresponding Debio 1143 dose (and nivolumab if on D15) will be omitted. Patients should be re-assessed (ideally every 48-72 hours, if clinically indicated) and treatment will only be resumed after all re-treatment criteria are met.
 
All patients who withdraw from treatment for any reason will be followed for safety up to 5 months (<math>\pm 15</math> days) after the last nivolumab infusion, complete resolution or stabilization of any ongoing toxicity, unless the patient starts a new treatment, end-of-life-care or withdraws consent.
 
If for any reason, treatment with nivolumab is temporarily withheld, Debio 1143 may be continued; however, at any time, and regardless of the reason, if nivolumab is permanently discontinued then Debio 1143 must also be withdrawn. If for any reason Debio 1143 is withheld temporarily, nivolumab will also be withheld until treatment may be resumed. Patients will not receive any further nivolumab infusions during the study until Debio 1143 treatment is resumed.

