## 5.2. DLT period and definition of DLTs

The DLT period is defined as Cycle 1\*.

DLT is defined as any of the following treatment-emergent adverse events (TEAEs) which are possibly, probably or definitely related to the combination treatment and occurring in Cycle 1 (1 cycle=4 weeks):

- Any Grade 4 or 5 hematologic toxicity, clinical or laboratory non-hematologic toxicity
- Febrile neutropenia any grade, Grade 3 thrombocytopenia if associated with bleeding or requiring platelet transfusion
- Grade 2 or higher cardiac or neurologic toxicities, pneumonitis that does not resolve within 3 days after starting steroids at adequate doses or that was recurrent upon steroid tapering or withdrawal, myasthenia gravis, myositis, polymyositis, Guillain-Barre syndrome (excluding peripheral purely-sensory neuropathies)
- Grade 2 or higher alanine transaminase (ALT)/ aspartate transaminase (AST) increase with a concurrent increase of total bilirubin  $\geq 2$  x upper limit of normal (ULN) and concurrent with alkaline phosphatase (ALP)  $\leq 2$  x ULN (Hy's law), in the absence of objective causes of biliary obstruction due to obvious disease-related causes
- Any other Grade 3 non-hematologic, treatment-related clinical toxicity lasting 3 or more days despite optimal supportive care, or requiring admission for appropriate medical management; hypersensitivity and/or infusion-related reactions are excluded if not reoccurring after appropriate pre-medication and/or prolonging infusion time
- Grade 3 non-hematologic laboratory value (excluding lipase, amylase and/or autoimmune endocrinopathies manageable by replacement therapies) if:
  - a. Symptomatic and
  - b. Medical intervention was promptly required to treat the patient, or
  - c. The abnormality led to hospitalization or
  - d. The abnormality did not resolve to at least Grade 1 within 2 weeks (including the steroid tapering period) despite adequate medical intervention/treatment
- A delay of >2 weeks due to drug-related toxicity in initiating Cycle 2
- Unable to complete at least 70% of the scheduled treatment, i.e. more than six Debio 1143 skipped doses in Cycle 1 due to treatment-related toxicity
- Required dose reduction in Cycle 1 or on Cycle 2 Day 1 or requirement for treatment withdrawal due to treatment-related toxicity (even if not meeting other DLT criteria)

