**Table 5-3 Re-treatment criteria**

Assessment	Debio 1143		Nivolumab
	Days 1 and 15	Days 2-10 or 16-24	Days 1 & 15
ECOG-PS	≤1	≤2	≤1
ANC	≥ 1.5 x10  /L	≥ 1.0 x10  /L	-
Platelets	≥ 100 x10  /L	≥ 75 x10  /L	-
Hemoglobin	≥ 9.0 g/dL	≥ 9.0 g/dL	≥ 9.0 g/dL
Total bilirubin	grade 1	grade 2 a	grade 1
AST/ALT	grade 1	grade 2 a	grade 1
Amylase or lipase increases	≤ Grade 3 b		-
Serum creatinine	≤ 2.0 x ULN	-	≤ 2.0 x ULN
Non-optimally treated, symptomatic immune-related AEs	-		≤ Grade 1 c
Any Debio 1143 drug-related AEs	≤ Grade 1 c	≤ Grade 2	-
Cardiac safety/ ECG	Baseline status		
βHCG urine pregnancy test (for women of childbearing age) d	Negative	-	Negative

ANC: absolute neutrophil count; AST/ALT: aspartate aminotransferase/alanine aminotransferase; AEs: adverse event(s); ECG: electrocardiogram; ECOG-PS: Eastern Cooperative Oncology Group performance status

- Provided that total bilirubin and/or ALT/AST levels were Grade 1 as per NCI-CTCAE v5.0 at the start of the corresponding cycle.
- As per NCI-CTCAE v5.0, Grade 3 is defined as amylase or lipase increases up to 5x ULN symptomatic or not; or above 5x ULN but asymptomatic
- Up to Grade 2 for alopecia, stable sensory neuropathy, fatigue/asthenia, skin toxicity or non-optimally treated nausea, vomiting or diarrhea or any grade endocrinopathy optimally treated by replacement therapy
- On every Day 1 for both Debio 1143 and nivolumab

From Cycle 2, if a patient does not meet the requirements for treatment continuation on Day 1 of any cycle, both study drugs will be withheld until recovery or for a maximum of 4 and 8 weeks (+1 week tolerance window) for Debio 1143 and nivolumab, respectively. After this delay-period, treatment should be withdrawn. If a delay occurs in initiating Cycle 2 and is due to any toxicity related to study drug, it will be considered as a DLT.

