If a patient does not meet the requirements for treatment continuation on any day other than D1 (D2-10 or D15-24) of any cycle, treatment will be immediately interrupted and the corresponding Debio 1143 dose (and nivolumab if on D15) will be omitted. Patients should be re-assessed, ideally, every 48-72 hours, if clinically indicated, and treatment will only be resumed after all re-treatment criteria are met. On D1, treatment can be delayed more than 3 days if required; in this case, the assessment schedule will shift accordingly, and all assessments planned for D1 will be performed on the day treatment is re-started. However, if treatment is interrupted during any day other than D1 and the re-treatment criteria are not met within 72 hours, treatment will be resumed only on D1 of the next cycle.

A maximum delay of 4 and 8 weeks (+1-week tolerance) for Debio 1143 and nivolumab, respectively, is allowed. After this delay-period, treatment will be withdrawn. Patients withdrawing from treatment for any reason will be followed for safety up to 5 months (±15 days) after the last nivolumab infusion, complete resolution or stabilization of any ongoing toxicity, unless the patient starts a new treatment, end-of-life-care or withdraws consent.

Patients experiencing immune-related AEs, that require withholding nivolumab infusions temporarily until resolution to at least Grade 1, may withhold nivolumab for a maximal period of up to 8 weeks (±1 week

tolerance). During this period, patients may continue to receive Debio 1143 as per protocol, if appropriate. Patients requiring more than 8 weeks ( $\pm 1$  week) of nivolumab interruption and those who permanently discontinue nivolumab for any reason, will discontinue Debio 1143 permanently and will be withdrawn from the study. The nivolumab dose will not be adjusted under any circumstances.

Patients experiencing any treatment-related grade 4 toxicity (clinically or laboratory, excluding grade 4 amylases and/or lipase and/or non-febrile neutropenia) will withdraw from treatment definitively without further reduction (see [section 8.3.2.1](#) for details).

Patients experiencing any other treatment-related toxicity fulfilling applicable DLT criteria (as shown below) at any time during the study must stop treatment and may only resume treatment after adequate recovery to re-treatment criteria.

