Treatment must be re-started with a Debio 1143 dose reduction. Individual patients may have up to two dose adjustments of 50 mg/d (each one) up to a minimum dose of 100 mg/d Debio 1143 (i.e. 1st dose reduction 150 mg/d, 2nd dose reduction 100 mg/day). Patients still requiring a dose adjustment with a dose of 100 mg/d will be withdrawn from the study. Once adjusted, Debio 1143 dose will not be re-escalated under any circumstances.

Up to 2 dose reductions must be implemented in the event of any of the following:

- Any Debio 1143-related Grade 4 hematologic toxicity
- Debio 1143-related febrile neutropenia any grade, or Grade 3 thrombocytopenia if associated with bleeding or requiring platelet transfusion
- Debio 1143-related grade 2 or higher alanine transaminase (ALT)/ aspartate transaminase (AST) increase with a concurrent increase of total bilirubin  $\geq 2$  x upper limit of normal (ULN) and concurrent with alkaline phosphatase (ALP)  $\leq 2$  x ULN (Hy's law), in the absence of objective causes of biliary obstruction due to obvious disease-related causes
- Any Grade 3, treatment-related, non-hematologic clinical toxicity lasting 3 or more days despite optimal supportive care, or requiring admission for appropriate medical management; hypersensitivity and/or infusion-related reactions are excluded if not reoccurring after appropriate pre-medication and/or prolonging infusion time
- Grade 3 non-hematologic laboratory value (excluding lipase, amylase and/or autoimmune endocrinopathies manageable by replacement therapies)
- A delay of  $>2$  weeks due to drug-related toxicity in initiating subsequent cycles, or a second delay lasting  $>24$  h but  $<2$  weeks
- Unable to complete at least 70% of the scheduled treatment, i.e. more than six Debio 1143 skipped doses during any cycle due to treatment-related toxicity or more than 2 treatment interruptions  $>24$  h but  $<6$  days

If for any reason Debio 1143 is withheld temporarily, nivolumab will also be withheld until treatment may be resumed. Patients discontinuing Debio 1143 definitively for any reason will also discontinue nivolumab study treatment.

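### Protocol section 5.4 counts any study-drug-related delay of Cycle 2 as a DLT, while the DLT definition in section 5.2 and the synopsis requires more than 2 weeks

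*Protocol*

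**What the plan says.** Three places in the protocol deal with a toxicity-related delay of Cycle 2.

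- **Section 5.2**, the section headed as the DLT definition, lists "A delay of >2 weeks due to drug-related toxicity in initiating Cycle 2". The synopsis DLT list has the same criterion with the same limit ("2 weeks due to drug-related toxicity in initiating Cycle 2").
- **Section 5.4**, in the paragraph after Table 5-3, says: "If a delay occurs in initiating Cycle 2 and is due to any toxicity related to study drug, it will be considered as a DLT".
- **Synopsis, Treatment duration**, carries the same paragraph as section 5.4 but ends at "After this delay-period, the patient should withdraw from treatment". It has no DLT sentence, so the any-delay rule appears in section 5.4 only.

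Later in section 5.4, a list introduced as the applicable DLT criteria again uses a limit of more than 2 weeks. After that figure it reads "weeks due to drug-related toxicity in initiating subsequent cycles, or a second delay lasting" more than 24 hours but less than 2 weeks.

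SAP section 18.1.2 takes DLTs from a yes/no question in the eCRF and has them confirmed at the dose decision. It states no delay threshold.

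**The concern.** The DLT count drives the 3+3 rules in section 5.1.1. It also drives the Part A primary endpoint (section 8.1.1.1), which requires DLTs in fewer than one-third of evaluable patients at the RP2D. Two current sentences classify the same patient differently, and neither refers to the other. An investigator holding a dose would work from section 5.4, while someone completing the DLT question might work from section 5.2. With three to six patients per dose level, one reclassified patient can change the decision. A reader of the results also cannot tell from the documents which rule lies behind the reported count.

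**Working it through.** **Step 1: which patients are in dispute.** Start with every study-drug-related delay of Cycle 2 and remove those that are DLTs under both rules.

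- Delays of more than 2 weeks are DLTs under both rules.
- Section 5.2 separately counts "Required dose reduction in Cycle 1 or on Cycle 2 Day 1", so a short delay that ends in a required reduction is a DLT under both rules.
- Section 5.4 requires a Debio 1143 adjustment after most Grade 3 related delays. The exceptions are neutropenia, thrombocytopenia, and non-optimally treated fatigue, diarrhea or nausea. Most Grade 3 delays are therefore removed as well.

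What remains is related delays of 2 weeks or less, with no required reduction and no other criterion met. These are mainly lower-grade or laboratory failures of the Day 1 limits in Table 5-3, plus the exempted Grade 3 events.

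**Step 2: an example.** Take drug-related platelets of 90 x10^9/L on Cycle 2 Day 1 (Table 5-3 limit: 100), no bleeding or transfusion, and restart after 5 days. Section 5.4 makes this a DLT; section 5.2 does not. No dose reduction follows from the section 5.4 list, which needs more than 2 weeks or a second delay. Cycle 2 is the first cycle to which the Day 1 hold applies, so this is a first delay.

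**Step 3: does the rule on interruptions of more than 3 days remove the example?** Section 5.4 requires dose adjustment after an interruption of more than 3 days. It uses different words for the two situations, however: "On D1, treatment can be delayed more than 3 days if required", as against "if treatment is interrupted during any day other than D1 and the re-treatment criteria are not met within 72 hours". On that wording a Day 1 hold is a delay, not an interruption, and the example stays in dispute. If a Day 1 hold were read as an interruption, delays of more than 3 days would require a reduction and so already be DLTs under section 5.2. Only delays of up to 3 days would then be disputed.

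**Step 4: the 72-hour text.** The end of section 5.4 describes a cycle delay as Day 1 moved by more than 72 hours. If that is the working meaning of a delay, shifts of 72 hours or less fall outside the any-delay sentence. With the alternative reading in step 3 as well, almost nothing stays in dispute. However, that text concerns re-planning of doses, and the section 5.4 list recognises delays from 24 hours, so a 72-hour floor is arguable.

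**Step 5: effect on decisions.** Let u be undisputed DLTs and d disputed delays. Section 5.2 counts u; section 5.4 counts u + d.

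| Dose | u | d | Section 5.2 rule | Section 5.4 rule |
|---|---|---|---|---|
| 200 mg, 6 evaluable | 1 | 1 | 1/6 = 16.7%: accept | 2/6 = 33.3%: reject |
| 200 mg, 6 evaluable | 0 | 2 | 0/6: accept | 2/6 = 33.3%: reject |
| 150 mg, first 3 | 0 | 1 | 0/3: escalate | 1/3: 3 more patients |

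Acceptance at 200 mg needs at most 1 DLT in 6, so the rules disagree only when u ≤ 1 and u + d ≥ 2. The first two rows are the minimal cases. At 150 mg a second DLT stops recruitment until the reasons are clarified; it does not by itself reject the dose.

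The documents give no rates for DLTs or for short Cycle 2 delays, so no probability of disagreement is offered.

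**The case against.** The strongest reply is that the protocol does have a governing definition. Section 5.2 is headed as such, the synopsis repeats its list, and section 5.4's own later list of applicable DLT criteria uses more than 2 weeks. Against these stands one sentence in a dose-modification paragraph. DLTs were also to be confirmed at each dose decision (SAP section 18.1.2), with ongoing data reviewed at DSMC meetings (protocol section 11.6.3), so the eCRF answer was not used unreviewed.

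Most of this stands. A reader might infer that the documents give no guide to which rule applies; they do, and it points to 2 weeks. What is missing is an express statement of precedence. Confirmation at the dose decision lowers the risk of an unnoticed error, but it does not say which threshold those confirming were to use.

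A reader might also infer that the 200 mg dose was wrongly accepted. The documents do not support that: they identify no patient with a short related Cycle 2 delay. Section 4.1.1 also makes overall safety, PK and compliance part of the RP2D determination.

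Finally, Part A is over: SAP section 4.3 records the futility of the Part B cohorts, and section 16.1 plans 200 mg. New wording can no longer alter a dose decision, so the report statement is the remedy with practical effect.

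**Conclusion.** This is an internal inconsistency in a decision rule. It is not a dispute about the 3+3 design or about the choice of 2 weeks. The section 5.4 sentence conflicts with section 5.2, the synopsis and section 5.4's own later list, and it should be brought into line with them. The disputed set is narrow, and narrower still on either alternative reading in steps 3 and 4. Within it, one patient is enough to reverse acceptance at 200 mg next to one undisputed DLT, or to add three patients at 150 mg. The conclusion rests on comparing the texts and on exact counting, with no assumed event rates. Whether any Part A patient was affected cannot be determined from the documents.

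**What to change.** **Protocol section 5.4.** Insert the limit of more than 2 weeks into the sentence and cross-refer to section 5.2, for example: *A delay of more than 2 weeks in starting Cycle 2 that is caused by study-drug-related toxicity counts as a DLT (see section 5.2).*

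**Study report.** State which delay rule was applied in Part A and whether any related Cycle 2 delay of 2 weeks or less occurred. If one did, give DLT counts by dose under both rules. The 200 mg count matters most: at a reported 1/6, one uncounted short delay would reverse acceptance under the section 5.4 sentence; at 0/6, two would be needed.

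**Cost.** One sentence, one report statement, and a recount of at most 12 planned evaluable Part A patients. Sample size and design are unchanged.

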**Table 7-2 Management of immune-related AEs**

NCI-CTCAE grade v5.0	Suggested management	Suggested follow-up
Gastrointestinal immune-related AEs: diarrhea and/or colitis		
Grade 1 Diarrhea: <4 stools/day over baseline Colitis: asymptomatic	
 
• May continue nivolumab therapy
 
• Evaluate symptomatic treatment (e.g. loperamide)
 
	
 
• Close monitoring for symptoms worsening
 
• Educate patient to report if worsening immediately
 
• If worsens: treat as Grade 2 or 3/4
 
• GI consultation may be needed for persistent cases (e.g. more than 4 weeks)
 

Grade 2 Diarrhea: 4 to 6 stools per day over baseline; IV fluids indicated <24 h; not interfering with activities of daily living Colitis: abdominal pain; blood in stool	
 
• Withhold temporarily nivolumab therapy until resolution to Grade 1
 
• Symptomatic treatment if infection is ruled out
 
• Consider GI consultation
 
• Consider 1 mg/kg/day prednisone or equivalent
 
	
 
• If improves to Grade ≤1: resume nivolumab therapy
 
• If persists ≥3 to 5 days or recurs: treat as Grade 3 or 4
 

Grade 3 to 4 Diarrhea (grade 3): ≥7 stools per day over baseline; incontinence; IV fluids ≥24 h; interfering with activities of daily living Colitis (grade 3): severe abdominal pain, medical intervention indicated, peritoneal signs Grade 4: life-threatening, perforation	
 
• Withhold temporarily nivolumab therapy for Grade 3, if first occurrence.
 
• Permanently discontinue study treatment for Grade 4 or recurrent Grade 3.
 
• 1 to 2 mg/kg/day prednisone IV or equivalent
 
• Add prophylactic antibiotics for opportunistic infections
 
• Consider lower endoscopy
 
• Consider early infliximab treatment (5-10 mg/kg) if symptoms are steroids-refractory after 2-3 days.
 
	
 
• If improves: continue steroids until Grade 1, then taper over at least 4-6 weeks; resume nivolumab therapy following steroids taper (for initial Grade 3).
 
• If worsens, persists ≥2 to 3 days, or recurs after initial improvement: add infliximab (5-10 mg/kg, if no contraindication)
 

NCI-CTCAE grade v5.0	Suggested management	Suggested follow-up

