### 7.7.1. Permitted medications

Permitted medications are:

- Supportive therapies to treat any emergent serious condition notably including medications against pain, nausea, vomiting, and diarrhea (per the Investigator's decision).
- Granulocyte colony-stimulating factor (G-CSF) and erythropoietic agents (per the Investigator's decision).
- Transfusions and blood-derived products as per local institutional guidelines.
- Bisphosphonates or denosumab as per local institutional guidelines in patients with symptomatic bone metastases, or malignant hypercalcemia or with increased risk of bone fractures.
- Steroids or anti-histaminic drugs according to local institutional standard protocols or guidelines (if any) for allergic reactions Grade  $\geq 2$  or prophylactically after C1D1.
- Patients requiring prolonged systemic steroids administration for any emerging medical cause at doses in excess of physiological replacement doses or more than prednisone 10 mg/d, should discontinue study treatment according to risk/benefit evaluation.
- Levetiracetam and pregabalin (per the Investigator's decision).
- Treatment of pain should be done according to severity and recommended drugs. Study-specific guidelines will be available.
- Any other medication for the well-being of the patient except those mentioned as prohibited medications at the Investigator's discretion.
- The use of oral contraceptives should be carefully evaluated during study treatment as well as the use of other drugs reported to cause liver injury.

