### 7.7.2. Prohibited medications

Attention should be paid to treatment that could influence the intended effects or mask side effects of study treatment. Use of drugs reported to cause liver injury should be carefully evaluated.

Concomitant use (until the EOT visit) of the following drugs and treatment modalities is prohibited (see [Appendix B: Prohibited medications](#) for the full list), except if they are indicated to treat any TEAEs related to study treatment ([i.e. anti-TNF- $\alpha$  therapy]). In this case, administration of these drugs is allowed and must be documented after interrupting Debio 1143 treatment.

- Strong P-gp inhibitors or inducers (see [Appendix B: Prohibited medications](#))
- Anti-TNF- $\alpha$  therapy (e.g. adalimumab [Humera®], etanercept [Enbrel®], infliximab [Remicade®], etc.)
- Other investigational agents other than mAbs within a 2-week period prior to initial dosing or while receiving Debio 1143
- Systemic corticosteroids, exceeding 10 mg/d of prednisolone or equivalent or physiological replacement doses of hydrocortisone. Note: topical corticosteroids for any indication, megestrol, or inhaled corticosteroids for reactive airway disease are permitted.

- Alcohol dependency defined as drinking greater than 100/140g (3.5/4.9 ounces) of alcohol per week for female/male patients, respectively
- Grapefruit juice or grapefruit-containing products and St John's Wort containing products
- Narrow therapeutic range or sensitive CYP 3A substrates or other drugs on the prohibited medication list (see [Appendix B: Prohibited medications](#)).

Restrictions also apply for P-gp substrates during Debio 1143 on-treatment periods (see [Appendix B: Prohibited medications](#)). In addition, narrow therapeutic range or sensitive CYP 2Cs (2C8, 2C9, 2C19), 2B6 or 1A2 substrates should be closely monitored. A list of drugs that are sensitive substrates of CYPs is available from website resources such as: Flockhart DA. Drug Interactions: Cytochrome P450 Drug Interaction Table. Indiana University School of Medicine (2007); <http://medicine.iupui.edu/clinpharm/ddis/table.aspx>.

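### For immune-related events treated with steroids above 10 mg/d or infliximab, the protocol does not say consistently whether Debio 1143 continues or is interrupted; if interrupted, a taper near 6 weeks can outlast its 4 (+1) week limit

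*Protocol*

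**What the plan says.** Several parts of the protocol speak to a patient whose nivolumab is held for an immune-related event and who needs steroids above 10 mg/d or infliximab.

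- **Synopsis, Treatment duration:** "If for any reason, treatment with nivolumab is temporarily withheld, Debio 1143 may be continued".
- **Section 5.4:** nivolumab may be held for up to 8 (±1) weeks for an immune-related event, and "During this period, patients may continue to receive Debio 1143 as per protocol, if appropriate".
- **Section 7.7.2:** the prohibited list, in force until the end-of-treatment visit, includes anti-TNF drugs (infliximab is named) and "Systemic corticosteroids, exceeding 10 mg/d of prednisolone or equivalent or physiological replacement doses of hydrocortisone". There is an exception when such drugs treat an event related to study treatment: "In this case, administration of these drugs is allowed and must be documented after interrupting Debio 1143 treatment". The exception carries a bracket, introduced by i.e., that names only anti-TNF-α therapy.
- **Section 7.7.1:** "Patients requiring prolonged systemic steroids administration for any emerging medical cause" above replacement doses or 10 mg/d of prednisone should discontinue study treatment, according to risk/benefit.
- **Section 8.3.2.1, item 5:** required or actual use of a prohibited medication is a reason to end treatment. The site contacts the medical monitor, and withdrawal is decided with the Sponsor.
- **Section 5.4, linkage and limits:** "If for any reason Debio 1143 is withheld temporarily, nivolumab will also be withheld until treatment may be resumed". The maximum delay is 4 weeks for Debio 1143 and 8 for nivolumab, each with 1 week of tolerance. Permanent discontinuation of either drug ends the other.
- **Table 7-2, gastrointestinal Grade 3-4 row:** on improvement, steroids continue to Grade 1, then "taper over at least 4-6 weeks; resume nivolumab therapy following steroids taper (for initial Grade 3". Six other situations have a taper of 1 month or 4-6 weeks after which nivolumab may resume.

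**The concern.** A site treating such an event finds a permission to continue Debio 1143, a condition that it be interrupted, a recommendation to discontinue, and an end-of-treatment reason. None refers to the others. Table 7-2 says what to do with nivolumab during a hold but not what to do with Debio 1143.

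The choice matters because the two drugs have different delay limits. If Debio 1143 continues, nivolumab has up to 8 (±1) weeks to come back. If Debio 1143 is interrupted, nivolumab stays off with it, and the shorter 4 (+1) week limit decides whether both end.

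At stake are a single usable instruction during a serious toxicity and the secondary endpoint of premature discontinuations and modifications due to adverse events (protocol section 8.1.2), which would partly reflect the passage followed rather than tolerability. There is also a possible route to the response rate. SAP section 17.2.1.3 requires a response to be confirmed before any non-permitted concomitant medication, and SAP section 6.5 (Category 6) excludes efficacy data assessed after prohibited drugs.

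**Working it through.** The plan derives no figure here, so there is none to reproduce. The check compares the passages and then computes durations.

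**1. The branches.**
- *Debio 1143 continues* (synopsis, section 5.4): the nivolumab limit of 8 (±1) weeks governs.
- *Debio 1143 is interrupted* (section 7.7.2, if the exception covers the drug used): nivolumab is also withheld, and the Debio 1143 limit of 4 (+1) weeks governs.
- *The exception covers anti-TNF drugs only*: steroids above 10 mg/d are prohibited outright, which conflicts with the 0.5-2 mg/kg/d courses in Table 7-2 and sends the case to section 8.3.2.1.

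**2. Time above 10 mg/d.** Weeks above 10 mg/d = I + D × (S − 10)/S, where I is weeks at full dose, D is the taper in weeks and S is the starting dose in mg/d.

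From the documents: mg/kg doses and tapers (Table 7-2), and 80 kg (the average weight behind the flat nivolumab dose, section 2.1). Assumed: 60 kg as the low end, I = 3-7 days (0.43-1 week), a linear taper to zero, and 1 month = 30.4375/7 = 4.35 weeks.

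For 1-2 mg/kg/d, S runs from 60 to 160 mg/d:
- 4-week taper: 0.43 + 4 × 50/60 = 3.76 to 1 + 4 × 150/160 = 4.75 weeks.
- 6-week taper: 0.43 + 6 × 50/60 = 5.43 to 1 + 6 × 150/160 = 6.63 weeks.

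| Table 7-2 situation that allows nivolumab to resume | Dose (mg/kg/d) | Taper | Weeks above 10 mg/d |
|---|---|---|---|
| Gastrointestinal Grade 3, first | 1-2 | 4-6 weeks | 3.8-6.6 |
| Pneumonitis Grade 2 | 1-2 | 4-6 weeks | 3.8-6.6 |
| Hepatic Grade 2, symptomatic | 0.5-1 | 4-6 weeks | 3.1-6.3 |
| Skin Grade 3, first; hypophysitis | 1-2 | 1 month | 4.1-5.1 |
| Persistent skin Grade 1-2; renal Grade 2 | 0.5-1 | 1 month | 3.3-4.8 |

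Against 5 weeks (limit plus tolerance), a 6-week taper from 1-2 mg/kg exceeds the limit throughout the range and a 4-week taper fits. One-month tapers fit except at the top of the skin Grade 3 and hypophysitis range. Against 4 weeks without tolerance, the 4-week and 1-month ranges from 1-2 mg/kg lie mostly above the limit. Several of the tapers are stated as minimum durations.

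**3. The pneumonitis taper.** The row gives both a rate (5-10 mg/week) and a duration (4-6 weeks). Together they remove 4 × 5 = 20 to 6 × 10 = 60 mg, against a starting dose of 60-160 mg/d. Only 60 kg at 1 mg/kg with the fastest rate and longest duration reaches zero. At 80 kg and 1 mg/kg, 80 − 60 = 20 mg/d remains after 6 weeks, and reaching 10 mg/d takes (80 − 10)/10 = 7 weeks. If the rate governs, even 60 kg needs (60 − 10)/10 = 5 weeks after induction.

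**4. When the clock starts.** The figures above start it with the steroids. Section 5.4 ties the withholding rule to a Day 1; on other days doses are omitted and, if recovery takes over 72 hours, resumed on the next Day 1. As an illustration, for steroids started on Day 15 the next Day 1 is 2 weeks later. If delay counts from there, the room is 2 + 5 = 7 weeks, more than the 6.6 above. The documents do not say which count applies.

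**The case against.** The strongest reply is that the permission is soft. Section 5.4 says Debio 1143 may continue if appropriate and as per protocol, which can be read as subject to section 7.7.2. That is a fair reading, but section 5.4 does not state it and the synopsis sentence has no such qualifier.

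The documents do not support several stronger conclusions that a reader might draw:

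- **That the Day 1 rule itself runs out during the taper.** Below Table 5-3, "both study drugs will be withheld until recovery or for a maximum of 4 and 8 weeks". Recovery there means meeting Table 5-3, which has no steroid criterion. Its immune-related row applies to nivolumab only and asks for Grade 1 or less, the point at which the gastrointestinal and pneumonitis tapers begin. Only section 7.7.2 can make the taper count against Debio 1143.
- **That Grade 3 colitis is a clean case of the permission to continue.** Section 5.4 separately requires stopping, and restarting at a reduced Debio 1143 dose, after related Grade 3 non-hematologic clinical toxicity lasting 3 or more days or needing admission. For such events this is a further instruction to reconcile.
- **That every Table 7-2 course overruns.** With the tolerance week, most of the shorter tapers do not. The table's columns are also headed as suggestions.
- **That like patients would be permanently withdrawn at one site and kept on at another.** Section 8.3.2.1 brings in the medical monitor and the Sponsor, and section 5.4 makes resumption after longer interruptions subject to Sponsor agreement where applicable. This limits divergence between sites, although the passages still give no rule.
- **That the response rate is biased.** No incidence is given. Protocol section 11.4.1.1 counts response until progression, new systemic therapy or cut-off, not until treatment stops, and section 8.3.2.2 keeps imaging patients without progression.

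**Conclusion.** The conflict is in the text and holds without any calculation: the permission to continue Debio 1143 in the synopsis and section 5.4 is not reconciled with sections 7.7.1, 7.7.2 and 8.3.2.1 when the event needs steroids above 10 mg/d or infliximab. Events managed without infliximab and at 10 mg/d or less are outside it.

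Its practical size depends on assumptions. If Debio 1143 is interrupted for all the time above 10 mg/d and the delay is counted from the start of steroids, tapers near 6 weeks from 1-2 mg/kg take 5.4-6.6 weeks against a limit of 4 (+1). The resume-nivolumab step is then unreachable for those gastrointestinal and pneumonitis courses, and some symptomatic hepatic courses also overrun. Shorter tapers mostly fit or straddle the limit. The result depends on weight, time at full dose, taper shape and the start of the clock.

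This should be fixed because the plan gives incompatible instructions in an expected toxicity and the discontinuation data depend on which is followed. The effect on ORR is indirect and unquantified, so the point does not by itself put the primary analysis in doubt.

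**What to change.** Reconcile the synopsis (Treatment duration), sections 5.4, 7.7.1, 7.7.2 and 8.3.2.1, and Table 7-2, so that one text, repeated consistently, states:

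- whether Debio 1143 is continued or held while steroids above 10 mg/d or infliximab are given for an immune-related event;
- whether the exception in section 7.7.2 covers steroids or only anti-TNF drugs;
- which delay limit applies, when its clock starts, and whether the steroid course counts;
- how this fits with the stop-and-reduce rule for Grade 3 events and with the Sponsor's role in withdrawal.

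Then check that each path in Table 7-2 that resumes nivolumab can be completed within the chosen limit, and reconcile the rate and duration in the pneumonitis taper. The clinical team decides the rule; the statistical requirement is only that it be single and explicit. The cost is protocol wording, with no added visits or patients.
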